6.6.4 Fidelity

Patients in the control arm should not be issued with an incentive spirometer or receive any teaching on its use. Adherence to random allocation (provision of incentive spirometer and associated teaching for those randomised to the intervention; and no provision of incentive spirometer for those randomised to the control) will be captured on the baseline CRF.

6.6.5 Adherence

A paper diary will be provided to participants in the intervention arm to record adherence to intervention use during their inpatient admission. These will be collected by local site staff on or after day 5 post randomisation, or on discharge, whichever is sooner, and data entered to the study database.

A CRF will also be provided to record any observed adherence, where feasible, in recognition of variable participant adherence to diaries in previous clinical trials (22). This includes any use of a spirometer in the participants randomised to the control arm (usual care). In cases where both participant diaries and staff-collected adherence data are available, participant entries will take precedence in the event of discrepancies; however, if only staff-collected data are complete, those will be used.

Participants in the intervention arm will be classed as adherent if they undertake a minimum of two incentive spirometer sessions a day, for a minimum of three days, in the five days post randomisation.

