6.6.3 Participant teaching

At the time of issue, a trained and delegated member of local site staff will instruct the participant in use of the incentive spirometer, in accordance with the manufacturer's instructions. Participants will be advised to use the incentive spirometer at least three times during the day and will be encouraged not to interrupt sleep for use. Participants will be advised to use the device for the first 5 days following injury.

The initial training session will be supplemented with an optional training video that participants will be able to access via their own personal devices, if they wish, and a paper education leaflet. The leaflet will be available in larger font if required. For patients who cannot speak English research teams will be encouraged to use local translation services to support training and device use where feasible. Competence in use of the incentive spirometer, judged as ability to use the device correctly without prompts (or with prompts for those supervised by a carer/staff member), will be assessed at the time

by the trainer. Up to two additional teaching sessions are permitted to promote independent use. Timescales for delivery of the initial and subsequent participant teaching sessions are shown in the schedule of assessments (section 7.8). Participants who do not achieve independent use (or supported use from carers/site staff where resources allow) after two teaching sessions will not receive any more teaching sessions but will remain in the trial.

The intervention is additive to standard clinical management which may include analgesic intervention, breathing exercises and mobilisation.

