11 ANALYSES

11.1 Statistical analysis

Analyses will be directed by a pre-specified Statistical Analysis Plan (SAP) and will be in line with CONSORT reporting guidelines for clinical trials. Participant flow will be reported in a CONSORT flow chart (²⁹). Participant baseline characteristics will be reported, overall and by randomised allocation, using descriptive statistics.

Continuous data will be summarised as mean and SD or median and inter-quartile range (IQR) if distributions are skewed. Categorical data will be summarised as number and percentages. The primary analysis will be conducted under the intention-to-treat approach, consisting of logistic regression of presence vs absence of pulmonary complications on allocation, adjusted for site, capacity status, and co-existing injury status (design variables). Results will be reported as an odds ratio with associated 95% confidence interval and p-value. Result will also be presented as an absolute difference and Number Needed to Treat for completeness. Secondary outcome analysis will be consistent with that described for the primary outcome, using a form of regression appropriate to the nature of the outcome being analysed (linear regression for continuous outcome, logistic regression for binary outcome etc), plus additional adjustment for baseline value of outcome where relevant. A repeat analysis of the primary outcome using a Complier Average Causal Effect analysis, with reporting of treatment effect based on adherence, will be considered. Sensitivity of the primary analysis to the impact of missing data will be explored.

Model validity will be checked using standard methods; if a model is a poor fit, alternative models or transformations will be explored.

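### The adherence source rule lets diary entries override sessions that staff witnessed, so a participant seen to meet the threshold can be classed non-adherent

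*Protocol*

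**What the plan says.** Section 6.6.5 of the protocol sets up two sources of adherence data.

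- The participant's source: "A paper diary will be provided to participants in the intervention arm to record adherence to intervention use during their inpatient admission". It is collected "on or after day 5 post randomisation, or on discharge, whichever is sooner".
- The staff source: "A CRF will also be provided to record any observed adherence, where feasible, in recognition of variable participant adherence to diaries in previous clinical trials". The same form is the place for any spirometer use seen in the control arm.

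The sources are ranked: when both are available, "participant entries will take precedence in the event of discrepancies; however, if only staff-collected data are complete, those will be used". The result feeds a two-way class. An intervention participant is adherent with "a minimum of two incentive spirometer sessions a day, for a minimum of three days, in the five days post randomisation".

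Section 6.6.5 does not define *complete* for either source. It does not say whether a blank diary day means no session or no information, does not allow sessions from the two sources to be combined, and has no class for unknown adherence.

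The class has one possible analytic use, in section 11.1: "A repeat analysis of the primary outcome using a Complier Average Causal Effect analysis, with reporting of treatment effect based on adherence, will be considered".

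**The concern.** The ranking does not fit what the two sources contain. A staff record of observed use is a floor: each entry is a session someone saw, and each gap may simply be a session nobody saw. The protocol adds this record because it expects diaries to be filled in unevenly, and then lets the diary prevail where the two disagree. Where the staff count is the higher one, this discards the evidence that the form was introduced to supply.

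The reverse problem arises if the staff record is used alone. A floor that reaches the threshold proves adherence. A floor that falls short proves little, yet a two-way class would score it as non-adherent.

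Other sections make gaps in both sources realistic. Section 6.7.2 accepts a wider window for the patient-reported outcomes because weekend staffing is thin. Section 6.6.3 makes staff support for device use depend on resources. Section 7.6 admits people with mild to moderate cognitive impairment, for whom diary gaps are plausible.

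At stake are the reported adherence rate and any complier analysis built on it. Section 4.1 wants the trial either to show benefit or to justify stopping the therapy. After a null result, the adherence rate shapes whether readers conclude that the device did not work or was not used.

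**Working it through.** **Reading the rule case by case (section 6.6.5)**

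1. The diary counts as complete but misses sessions, and staff saw more. The diary prevails and the witnessed sessions are dropped.
2. The diary is incomplete and the staff data are complete. The staff data are used, so the rule gives protection here.
3. Both are partial and differ. The exception needs complete staff data, so on the plain wording the diary prevails.
4. There is no usable diary and the staff log is partial. The text fixes no class unless the log is called complete; if it is, a minimum count sets the class.

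**The protocol's own figures**

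The protocol states no adherence rate and no complier effect. Its sample size is untouched: 50% v 30%, two-sided 5% alpha and 90% power give 124 per arm, or 248, and 248/0.90 = 275.6, rounded up to 276. Both stated figures reproduce.

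**How often under-recording changes the class**

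Inputs: the threshold of section 6.6.5, and a participant following section 6.6.3 ("Participants will be advised to use the incentive spirometer at least three times during the day") with three sessions a day for five days. Assumption: each session is recorded independently with probability q.

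- Chance that a day reaches the threshold: d = 3q²(1−q) + q³.
- Chance of being classed adherent: P(at least 3 of 5 days), binomial with probability d.

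Example, q = 0.4: d = 3 × 0.16 × 0.6 + 0.064 = 0.352. Then 10 × 0.352³ × 0.648² + 5 × 0.352⁴ × 0.648 + 0.352⁵ = 0.183 + 0.050 + 0.005 = 0.238.

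| Share of sessions recorded | Correctly classed adherent |
|---|---|
| 20% | 1% |
| 30% | 7% |
| 40% | 24% |
| 50% | 50% |
| 60% | 76% |
| 70% | 93% |
| 80% | 99% |

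The margin over the threshold matters. At 80% recorded, someone doing two sessions on all five days is classed correctly in 75% of cases, and someone doing exactly two on three days in 26%.

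**Diary precedence against the larger daily count**

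With both sources present, a day reaches the threshold under the larger count with probability 1 − (1 − d_diary)(1 − d_staff).

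- Diary records 50%, staff see 30%: d = 0.500 and 0.216. The combined value is 1 − 0.500 × 0.784 = 0.608. Correct class: 50% under precedence, 70% under the larger count.
- Diary records 60%, staff see 50%: d = 0.648 and 0.500. The combined value is 1 − 0.352 × 0.500 = 0.824. Correct class: 76% against 96%.

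**Effect on a complier estimate**

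Risk-difference scale: complier effect = ITT difference / (recorded adherence in the intervention arm − recorded use in the control arm). Only the 20-point difference comes from the protocol.

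- *Staff-only limb.* Assume true adherence 70%, 30% of diaries unusable, staff seeing 40% of sessions, usable diaries correct, and no control use. Recorded adherence = 0.70 × (0.70 + 0.30 × 0.238) = 0.540. The complier effect is 20/0.540 = 37.0 points, against 20/0.70 = 28.6, about 30% too large.
- *Range for that limb.* 20% unusable and 50% seen: 0.70 × (0.80 + 0.20 × 0.50) = 0.630, giving 31.7. 40% unusable and 30% seen: 0.70 × (0.60 + 0.40 × 0.071) = 0.440, giving 45.5.
- *Precedence limb.* True adherence 70%, everyone with both sources, diary 60% and staff 50%. Precedence: 20/(0.70 × 0.76) = 37.6. Larger daily count: 20/(0.70 × 0.96) = 29.8.

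**Conditions that reverse the direction**

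- True adherence 80% (true effect 20/0.80 = 25.0), no adherer missed, half of non-adherers over-reporting: recorded 0.80 + 0.20 × 0.50 = 0.90, giving 22.2.
- True adherence 80% with 10% control use that nobody records: true effect 20/(0.80 − 0.10) = 28.6, estimated 20/0.80 = 25.0. If only 80% of adherers are also recorded, the estimate is 20/0.64 = 31.3.

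**The case against.** **The rule has an exception.** A reader might infer that any incomplete diary overrides what staff saw. The text does not support that, because complete staff data prevail over an incomplete diary. This stands. It protects little, though, because *complete* is undefined and a log of observed use will rarely be complete.

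**A partial staff log is not complete, so the rule does not say it yields non-adherence.** This also stands. The staff-only limb, and with it the 37 v 29 example, assumes that a partial log is put through the threshold as if it were a full count. That is an inference from an undefined term. The precedence limb does not depend on it.

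**Inflation is not certain.** A reader might infer that the complier effect must be too large. The documents do not support that either. Diary over-reporting passes through the same rule and lowers the estimate, as does control-arm use that staff miss. With 80% or more of sessions recorded, someone doing three a day is rarely misclassified.

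**Preferring the diary is defensible when staff see only part of the use.** That is so when the diary count is the higher one, and the larger daily count keeps the diary there too. It gives no reason to discard a witnessed session when the staff count is higher. The larger count can only raise recorded use and cannot correct an over-report, but it adds none beyond those already in the diary.

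**Little depends on it.** The primary analysis is ITT under a treatment-policy estimand, the summary measure is an odds ratio rather than the risk difference used above, and the complier analysis is only to be considered. A near-zero ITT difference also stays near zero when divided by a smaller adherence rate. All of this is right and limits the weight of the point.

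**Conclusion.** The point holds in a limited form. Section 6.6.5 itself fixes a source ranking under which witnessed sessions can be set aside and a participant seen to meet the threshold can be classed non-adherent. If staff data are used alone, they can establish adherence but cannot reliably rule it out.

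The size cannot be known from the protocol, which gives no diary-completion or observation rates. Under independent recording and use at three a day, replacing precedence by the larger daily count moves correct classification from 50% to 70% or from 76% to 96% in the two settings shown. If under-recording dominates, reported adherence is too low and a complier effect too large. The 37 v 29 points, and the range of about 32 to 46, are illustrations on assumed rates and not predictions.

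The consequence is confined to the adherence summary and a possible supporting analysis. The ITT primary analysis and the sample size are unaffected.

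**What to change.** Replace the precedence sentence in section 6.6.5 with wording such as:

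*For each day, the number of sessions is the larger of the diary count and the staff-observed count; blank diary days are missing, not zero. Where no usable diary exists, staff-observed data may classify a participant as adherent; if they do not reach the threshold, adherence is unknown, with bounds assuming that all unknown participants are adherent and that all are non-adherent.*

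Define *complete* for each source and what makes a diary usable. Report adherence by source as a sensitivity check, and use the same derived variable in the adherence summary and in any complier analysis. Settle this before the data are seen. The threshold itself need not change.

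The cost is a short text change and one derived variable, with no new data collection. The downside is that some participants will have unknown adherence, so any complier estimate comes with a range. Over-reporting in diaries still counts as it does now.

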6.7 Outcomes

6.7.1 Primary outcome

The primary outcome is a binary measure of the onset of one or more new pulmonary complications within five days of randomisation. This will be adapted from the outcome proposed by the European Society of Anaesthesiology and Intensive Care Medicine as a consensus definition (Table 2) (23). Patients with evidence of pulmonary complications prior to randomisation will not meet the primary outcome. Any deaths occurring within the first 5 days following randomisation will meet the criteria for the primary outcome.

Table 2: Pulmonary Complications

Complication	Definition
Respiratory Infection	Patient has received antibiotics for a suspected respiratory infection and met one or more of the following criteria: new or changed sputum, new or changed lung opacities, fever, white blood cell count $>12 \times 10^9 \text{ l}^{-1}$

Respiratory failure	PaO ₂ <8kPa (60mmHg) on room air, a PaO ₂ :FiO ₂ ratio <40kPa (300mmHg) or arterial oxyhaemoglobin saturation measured with pulse oximetry <90% (or <88% for patients with known chronic respiratory disease) and requiring oxygen therapy
Pleural effusion	Chest radiograph demonstrating blunting of the costophrenic angle, loss of sharp silhouette of the ipsilateral hemidiaphragm in upright position, evidence of displacement of adjacent anatomical structures or (in supine position) a hazy opacity in one hemithorax with preserved vascular shadows
Atelectasis	Lung opacification with a shift of the mediastinum, hilum or hemidiaphragm toward the affected area, and compensatory over-inflation in the adjacent non-atelectatic lung
Pneumothorax	Air in the pleural space with no vascular bed surrounding the visceral pleura
Bronchospasm	Newly detected expiratory wheezing treated with bronchodilators
Aspiration pneumonitis	Acute lung injury after the inhalation of regurgitated gastric contents

Primary outcome data will be collected by research practitioners from inpatient hospital records at five days and reviewed/confirmed by the local Principal Investigator. For the small number of patients discharged in the interim, online GP records (routinely available at recruiting sites) will be checked for evidence of pulmonary related events (e.g., pneumonia).

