6 TRIAL DESIGN AND SETTING

6.1 Trial schema

6.2 Trial design

Pragmatic, multicentre, open-label, parallel two-group randomised controlled superiority trial. Older adults being admitted with traumatic rib fractures will be randomly assigned in a 1:1 ratio.

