6.7.3 Estimands

Estimand component	Definition
Population	All participants meeting eligibility criteria and randomised to a treatment arm, with complete primary outcome data, and baseline data included in primary analysis model (i.e., complete case intention to treat population)
Treatment condition	Incentive spirometry in addition to usual care vs usual care without incentive spirometry, regardless of intervention compliance
Endpoint	Onset of new pulmonary complications within 5 days of randomisation (binary outcome)
Summary measure	Odds ratio
Handling of intercurrent events	Intercurrent events will be handled using a Treatment Policy approach (sensitivity analyses may be used to explore different approaches)

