6.7.4 Target sample size (with calculation/justification)

276 patients recruited from 12 UK hospitals. The incidence of pulmonary complications in this population has been observed at 50% (5). In the only RCT of incentive spirometry for trauma identified, Sum and colleagues (8) observed a 50% absolute risk reduction in pulmonary complications, but this effect size was estimated with a large margin of error and may not be generalisable. A more conservative estimate of a 20% reduction in the intervention arm has, therefore, been proposed as a target effect size that is both achievable and meaningful to detect. Our PPI group agree this is a reasonable effect size to change practice. To detect a reduction in pulmonary complications from 50% in the control group to 30% in the intervention group with 90% power at a 5% alpha level, an analytical sample size of 248 is required. To allow for 10% attrition a total sample size of 276 is required. Most participants will remain inpatients at five days, and GP online records are routinely available for any that have been discharged. The only anticipated loss to primary outcome follow-up will be those who are admitted out of area and discharged within five days to another region where GP records may not be accessible. Sample size calculation was conducted using the 'power' command in Stata (version 18).

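### The rule on complications present before randomisation is written per patient: read literally, it discards new non-fatal complications and conflicts with the death rule

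*Protocol*

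**What the plan says.** **Outcome.** Protocol section 6.7.1 defines a binary event: at least one new complication from Table 2 arising in the five days after randomisation. Two sentences qualify it. The first is "Patients with evidence of pulmonary complications prior to randomisation will not meet the primary outcome". The second is "Any deaths occurring within the first 5 days following randomisation will meet the criteria for the primary outcome". Neither refers to the other.

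**Who can be enrolled.** Section 6.5.1 screens lung state only through oxygen saturation and intubation. A pneumothorax, effusion, atelectasis or infection already present does not exclude. Section 7.3 allows up to 24 hours between admission and randomisation.

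**Who is analysed.** The estimand population in section 6.7.3 (Estimands) is "All participants meeting eligibility criteria and randomised to a treatment arm", provided that outcome and model data are complete. The model in section 11.1 adjusts for site, capacity status and co-existing injury, not for prior complications.

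**Sample size.** Section 6.7.4 is planned "To detect a reduction in pulmonary complications from 50% in the control group to 30% in the intervention group" and arrives at 248 analysed participants (5% alpha, 90% power), or 276 recruited. It makes no allowance for participants with prior complications. It does not say how the feasibility trial that supplied the 50% handled them.

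**The concern.** Several Table 2 components (pneumothorax, pleural effusion, atelectasis) can be findings of the injury itself, visible on the imaging that shows the fractures. Section 4 mentions lung injury underlying rib fractures, and section 8.5 lists pneumothorax among the events anticipated in this population. The affected group is therefore plausible, though its size is not given.

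Three things are at stake:

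- **The question asked.** Taken literally, the rule removes new non-fatal complications in this group, which are the events the device is meant to prevent. Forced non-events lower both arms' rates and shrink the absolute difference.
- **Consistency.** The wording allows a per-patient and a per-complication reading. Staff at 12 sites could score identical participants differently.
- **Timing of the judgement.** Section 6.7.1 has research practitioners extract the outcome from records at day 5, with confirmation by the local principal investigator. Section 7.12 says local teams cannot be blinded, and the protection it offers, self-report, does not cover a record-based outcome. The baseline CRF items listed in section 7.9 do not name Table 2 status, although that list is expressly not exhaustive. As written, whether a complication was already present can be decided after the allocation is known.

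**Working it through.** **1. The text applied to three participants**

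| Participant | Onset definition | Prior-complication sentence | Death sentence |
|---|---|---|---|
| Pneumothorax at baseline, nothing new by day 5 | Non-event | Non-event | Not applicable |
| Pneumothorax at baseline, pneumonia on day 3 | Event | Non-event | Not applicable |
| Pneumothorax at baseline, dies on day 4 | Depends on course | Non-event | Event |

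The sentences agree only in the first row. No order of precedence is given for the other two.

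**2. The plan's own figure**

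Inputs from section 6.7.4: 50% v 30%, 90% power, 5% alpha, 10% attrition. Section 6.2 gives 1:1 allocation. Sidedness is not stated; two-sided is assumed because it reproduces the result.

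With p̄ = (p1 + p2)/2, the number per arm is

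n = [1.96·√(2p̄(1−p̄)) + 1.2816·√(p1(1−p1) + p2(1−p2))]² / (p1 − p2)²

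= [1.96·√0.48 + 1.2816·√0.46]² / 0.04 = 4.96/0.04 ≈ 124.

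That gives 248 analysed, and 248/0.9 = 275.6, so 276. Both stated figures reproduce. (A continuity correction would give 134 per arm, so it was not used.)

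**3. Effect of forcing a share q to non-event**

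Two assumptions, neither in the documents: a share q of each arm has a prior complication, and 50% v 30% are the rates in the rest. Early deaths in the q group are set aside at first. Then p1 = 0.50(1−q), p2 = 0.30(1−q), and

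power = Φ{[(p1−p2)√n − 1.96·√(2p̄(1−p̄))] / √(p1(1−p1) + p2(1−p2))}.

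Example, q = 20% and n = 124: p1 = 0.40, p2 = 0.24, p̄ = 0.32. The numerator is 0.16·11.136 − 1.96·√0.4352 = 0.489 and the denominator is √0.4224 = 0.650. Φ(0.752) = 77.4%.

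| q | Rates | Difference (points) | Power, 248 analysed | Power, all 276 analysed | Analysed N for 90% (with 10% attrition) |
|---|---|---|---|---|---|
| 0 | 50 v 30 | 20 | 90.0% | 92.8% | 248 (276) |
| 5% | 47.5 v 28.5 | 19 | 87.4% | 90.6% | 272 (303) |
| 10% | 45 v 27 | 18 | 84.4% | 88.0% | 296 (329) |
| 20% | 40 v 24 | 16 | 77.4% | 81.7% | 354 (394) |
| 30% | 35 v 21 | 14 | 69.2% | 73.8% | 430 (478) |

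With 248 analysed, power drops below 80% once q exceeds about 16%. With all 276 analysed, 90% is kept up to q of about 6%.

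**4. Deaths counted.** If 2% to 5% of the q group die by day 5 in both arms (an assumption), power at q = 20% with 248 analysed is 77.1% to 76.7%. The death sentence does not recover the loss.

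**5. The alternative premise.** If the feasibility trial's 50% was counted under the same per-patient rule, the forced non-events are already in it, and power stays at 90.0% with 248 analysed.

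**The case against.** **The sentence may have been meant per complication.** The endpoint is described throughout as new onset, so the sentence could mean only that something already present does not itself score. On that reading the day-3 pneumonia counts and nothing is lost. This is a fair reading of the intent, but the words do not say it, and sites will apply the words.

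**Lost power is not demonstrated.** A reader might infer that the trial is underpowered. The documents do not support that. They give no value for q, and section 4 describes the feasibility patients as going on to develop complications, which suggests onset after entry. They do not show how prior status was handled there. Section 6.7.4 also expects little loss to primary follow-up, so the 276 column may be nearer the truth than the 248 column. This objection stands: the power figures are conditional.

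**Such participants are not wholly barred from being events.** A reader might infer that they can never count. The death sentence, taken as written, makes a death by day 5 an event, so the rule reaches only non-fatal complications.

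**Biased removal of events is not shown.** The rule applies to both arms alike, so in itself it dilutes rather than favours one arm. Eligibility imaging precedes consent (section 15.2), and the baseline CRF may already capture what is needed. What stands is that the protocol does not require prior status to be fixed before allocation is known.

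**Conclusion.** The defect is in the definition of the primary outcome and is established from the text. The prior-complication rule is worded per patient, contradicts the onset definition for a participant with a different new complication, and contradicts the death sentence for one who dies. Eligibility, estimand and model neither exclude, remove nor adjust for these participants. It should be corrected before any outcome is scored.

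The size is uncertain. On the premise that 50% v 30% applies to participants free of prior complications, the cost with 248 analysed runs from about 3 points of power at q = 5% to about 21 points at q = 30%. On the premise that the 50% was measured under the same rule, there is no shortfall against the planned 90%, but new complications in this group still go uncounted. The stated 248 and 276 are arithmetically correct on their own inputs.

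**What to change.** In section 6.7.1, replace the prior-complication sentence with a per-complication rule:

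- A Table 2 type present at randomisation does not itself count.
- Any Table 2 type not present at randomisation and arising within five days counts, whatever else was present.
- Death by day 5 counts regardless of prior status.

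Record Table 2 status type by type, from existing notes and imaging, before the allocation is returned. Section 7.7 already requires data entry at that step.

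In section 6.7.4, state how the feasibility trial's 50% treated participants with prior complications. If the per-patient rule is kept deliberately, say so, give death precedence explicitly, and restate the power for a stated q.

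The cost is a short rewording and a few extra baseline CRF items, with no extra participants for the rewording itself. One caveat: a participant with a type already present has fewer types left to count, so the new rule does not guarantee 50% v 30% in that group.
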